# 9.3 Serious Adverse Event Reporting Procedures:

All SAEs must be reported in the electronic CRF within one working day of discovery or notification of the event. Initial SAE information and all amendments or additions must be recorded on a Serious Adverse Event Report form.

Description of SAEs reporting is included in Appendix C.

# 10. STATISTICAL CONSIDERATIONS:

# 10.1 Study Design:

This is a prospective randomized, open-label (unblinded), controlled, parallel group multi-center study performed in Denmark. Patients are recruited following identification from Danish registries as well as from outpatient clinics, and after hospitalizations. The study will recruit individuals who live in the Capital Region of Denmark, Region Zealand or the Southern Region of Denmark. The study is expected to conclude when 279 strokes have occurred or 6,000 study subjects have been followed for at least 36 months, which is expected to be approximately 5 years after enrolment of the first subject. Subjects meeting the eligibility criteria will be randomized to either receive an ILR (ILR group) or not ie, continue standard care (control group). The randomization occurs at a ratio of 1:3 (ILR group vs.

control group) as described in section 5.2. The LOOP study will comply with the standards of the CONSORT Statement. The study design is further described in section 3.

# 10.2 Study Endpoints and Subsets:

# **10.2.1 Primary Endpoint:**

Efficacy (time to at least one of the components of the combined primary endpoint):

- adjudicated stroke or
- adjudicated systemic arterial embolism

# 10.2.2 Secondary Endpoints:

- Composite endpoint of time to adjudicated stroke, or systemic arterial embolism, or cardiovascular death
- Time to death by any cause
- Time to cardiovascular death
- Time to adjudicated ischemic stroke
- Time to adjudicated transitory ischaemic attack
- Time to diagnosis of atrial fibrillation
- · Time to diagnosis of atrial flutter

# 10.2.3 Other Endpoints:

- Time to adjudicated intracranial hemorrhage not classified as stroke
- Time to major bleeding as defined by the International Society on Thrombosis and Haemostasis criteria
- Time to complications related to device implantation (Infection, hematoma, or other complication related to device implantation requiring intervention)

# 10.2.4 Supplementary Endpoints:

- Time to first acute (non-elective) hospitalization for stroke, systemic arterial embolism,
   transient ischemic attack, bleeding, cardiac disease, or complications, requiring an overnight
   stay in hospital or resulting in death
- Time to first admission for acute coronary syndrome or myocardial infarction
- Time to first implantation of cardiac pacemaker or defibrillator (with or without resynchronization therapy)
- Time to first ablation of cardiac arrhythmia
- Development of AF burden
- Development of other cardiac arrhythmias
- ECG markers in predicting AF
- Changes in health economic costs
- Change from baseline QoL, and Quality Adjusted Life Years

- MRI: Change in occurrence of brain infarcts and white matter hyper-intensity
- MRI: Left atrial size, fibrosis, and function and the association with stroke and AF
- Safety aspects (such as infections) of ILR implants
- Inflammation markers and cardiac hormones and their prediction of AF and stroke
- Changes in cognitive dysfunction evaluated by MoCA forms
- Genetic prediction of AF and stroke
- Echocardiographic prediction of AF and stroke

#### 10.2.5 Subsets:

# **Efficacy Analysis Set:**

Efficacy analysis will be performed on the intent to treat (ITT) subject set, defined as comprising all subjects randomized. Efficacy analysis will include all available follow-up data from all randomized subjects. In addition sensitivity analysis may be carried out based on the un-treatment subject set, which is defined as subjects not receiving ILR regardless of randomization.

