# Sample size:

In total 6,000 subjects will participate: 1,500 randomized to receive an ILR (ILR group) and 4,500 randomized to receive standard care (control group).

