#### 3. EXPERIMENTAL PLAN:

#### 3.1 Study Design:

This is a prospective randomized, open-label (unblinded), controlled, parallel group multi-center study performed in Denmark. Participants are recruited following identification from Danish registries as well as from outpatient clinics, and after hospitalizations. The study will recruit individuals residing in Region Zealand, Region of Southern Denmark or the Capital Region of Denmark. Potentially, the study region will be increased to cover other parts of Denmark. Participants are randomized to either receive an ILR (ILR group) or not receive one (control group). The randomization occurs at a ratio of 1:3 (ILR group vs. control group). The LOOP study will comply with the standards of the CONSORT Statement. 

After successfully completing all screening and baseline procedures, subjects will be randomized in a ratio of 1 to 3 to receive an ILR or usual control. The ILR will be programmed according to study recommendations (see section 6.2).

The study flow chart is given in Appendix A and the study endpoints are defined in section 10.2. A steering committee (SC) will oversee the conduct of the study. Composition and roles of this and other committees are described in section 10.7.

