# 3.3 Number of Study Subjects:

Participants in this clinical investigation shall be referred to as subjects or patients. Approximately 6,000 subjects will be randomized in a ratio of 1:3 to receive an ILR (ILR group) or continue standard care regimen (control group).

It is expected, that the randomization period will last for 2 years. The decline rate is estimated to be <10 %. The cross over from control to the ILR group is expected to be <10 %, since an ILR implant is generally assumed to require a syncope or definite clinical suspicion of arrhythmia or a wish to quantify arrhythmia burden. Subjects discontinuing from the study prematurely will remain in endpoint follow-up unless consent is withdrawn. Statistical considerations are provided in section 10.3.

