#### 10.3 Sample Size Considerations:

We expect that 30% of the participants will have documented AF episodes lasting ≥6 minutes (and per protocol qualifying for OAC) during ILR monitoring for at least three years. The study population is expected to have a stroke rate of 0.7%/year in non-AF patients, and 2%/year in AF patients not treated with OAC. While we expect the number of AF-related strokes to be reduced by OAC, we assume that strokes unrelated to AF will not be influenced by this. We also include the assumption that 3% of all participants in the control group will become diagnosed with AF and start OAC. The annual rate of the primary end point in the control group is thus expected to be 1%. Finally, we expect that 5% in the ILR group will not be monitored due to refusal of ILR implantation or ILR explantation due to discomfort. These patients will participate at the same risk as patients in the control group and will be included in the analysis of the primary endpoint according to the intention-to-treat principle. We thus expect the overall hazard ratio to be 0.65. To analyse this reduction in the primary endpoint with a 2-sided α-level of 0.05 and a power of 80% in a 1:3 intervention:control-randomized population, we will need 279 primary events. Follow-up duration will be adjusted to accommodate the number of primary events. With an assumed length of inclusion period of 1-2 years and a median follow-up up 4 years, 6000 subjects will be needed.

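### As worded, the sensitivity set in Section 10.2.5 contains no ILR recipient, so the optional analysis based on it cannot contrast ILR with no ILR (minor; one sentence to correct)

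*Protocol*

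**What the plan says.** Section 3.1 defines the randomised contrast: "Participants are randomized to either receive an ILR (ILR group) or not receive one (control group"). The synopsis gives the arm sizes: "1,500 randomized to receive an ILR (ILR group) and 4,500 randomized to receive standard care (control group").

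Section 10.2.5 names two sets for efficacy. The main one is standard: "Efficacy analysis will be performed on the intent to treat (ITT) subject set, defined as comprising all subjects randomized". The second is optional: "In addition sensitivity analysis may be carried out based on the un-treatment subject set". The same sentence goes on to define it, as the "un-treatment subject set, which is defined as subjects not receiving ILR regardless of randomization".

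Two other sections bear on who would be in it. Section 10.3 states that "we expect that 5% in the ILR group will not be monitored due to refusal of ILR implantation or ILR explantation due to discomfort", and adds that these patients carry the control group's risk and stay in the intention-to-treat analysis. Section 3.3 states: "The cross over from control to the ILR group is expected to be <10" per cent. It explains that an ILR in a control would generally call for syncope, a definite suspicion of arrhythmia, or a wish to quantify arrhythmia burden.

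No on-treatment, per-protocol or as-treated set that includes ILR recipients is defined elsewhere in the protocol. The covariate-adjusted cause-specific Cox model in Section 10.6.2.1 is a supportive model, not another analysis set.

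**The concern.** A sensitivity analysis based on device actually received needs people who received the device. This definition keeps only those who did not. Implanted ILR-arm subjects and implanted controls both drop out, leaving people who were never monitored by the study device.

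The set's name does not settle the matter. Un-treatment is not a recognised set name. It resembles on-treatment, but the definition attached to it describes the untreated. A statistician who followed the text would have to either run an uninformative comparison or guess what was meant. If the guess is made after the data are seen, the choice of set is post hoc. An analysis plan that copied the sentence would carry the problem forward.

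The stake is limited to this optional analysis. Refusal, explantation and crossover all move the intention-to-treat estimate away from the effect of the device as received, so a look by actual receipt is a reasonable thing to want. The protocol does not, however, state that as the purpose of the set.

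**Working it through.** **No figure to reproduce.** The protocol gives no size for this set. Its 279 events come from the main comparison and do not enter here. For completeness, Freedman's formula at 1:3 gives (1.960 + 0.842)² × (1 + 0.65/3)² / [(1/3) × (1 − 0.65)²] ≈ 285, within 3% of 279.

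**Inputs**
- Arm sizes 1,500 and 4,500 (synopsis; 1:3 in Sections 3.1, 3.3, 10.1 and 10.3. Section 5.4 says 1:9, a separate discrepancy; 1:3 is used here).
- ILR arm not monitored: 5% (Section 10.3). This includes explants, who did receive an ILR, so 5% is an upper figure for never implanted.
- Control crossover below 10% (Section 3.3), taken as a range of 0 to 10%.
- Control event rate 1% per year and median follow-up 4 years (Section 10.3).
- Unmonitored ILR-arm patients at control risk (Section 10.3).

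**Composition of the set as written**
- ILR arm: at most 0.05 × 1,500 = 75. At least 1,500 − 75 = 1,425 implanted subjects are excluded.
- Controls: 4,500 × (1 − 0.10) = 4,050, up to 4,500.
- Total: 4,125 to 4,575, with the ILR arm contributing 75/4,575 = 1.6% to 75/4,125 = 1.8%.
- ILR recipients: 0.

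**Comparison by randomised arm**
- Expected events: 75 × 4 × 0.01 = 3, against 4,050 × 4 × 0.01 = 162 up to 4,500 × 4 × 0.01 = 180.
- Both groups are unmonitored and at the same assumed risk, so the expected hazard ratio is 1.
- SE(log HR) = √(1/3 + 1/162) = 0.583, or √(1/3 + 1/180) = 0.582. The 95% interval extends by a factor of exp(1.96 × 0.58) ≈ 3.1 either way.
- Even if a hazard ratio of 0.65 held in this set, Schoenfeld power with 183 events and an ILR share p = 0.0164 is Φ(√(183 × 0.0164 × 0.9836) × |ln 0.65| − 1.96) = Φ(0.74 − 1.96) ≈ 11%.

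**Comparison by ILR receipt**
- The group that received an ILR is empty, so there is nothing to estimate.

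**The case against.** The strongest reply is that this is a drafting slip in an analysis that may never be run. Section 10.2.5 makes the sensitivity analysis optional, the principal analysis is intention to treat on all randomised subjects, and no type I error or sample-size figure depends on the set. All of that stands, and it is why the point is minor.

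A second reply is that disregarding the randomised arm is as-treated language. The sentence may describe only the untreated half of an as-treated comparison, with ILR recipients as the implied other half. That may be what was meant, but the sentence names no second group and says the analysis is based on this set, so it would still need rewording.

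A third reply is that Section 10.2.5 names a set and not a contrast, so the 75-subject comparison is the reader's construction. That is fair. The figures show what the literal text would yield, not an analysis the protocol prescribes.

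Two stronger readings are tempting and are not supported:
- A reader might infer that the trial has no usable check on its intention-to-treat result. The statistical analysis plan is not available here and may define further sets; only the wording of this one can be faulted.
- A reader might infer that the set was designed to examine dilution by refusal and crossover, and that a misleading estimate will be presented as a robustness check. The protocol states no purpose for the set and does not say how its result would be reported. Section 10.3 already counts the 5% not monitored among the assumptions behind the hazard ratio of 0.65.

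**Conclusion.** The definition is wrong as written, and nothing else in the protocol corrects it. Taken literally, the set holds no ILR recipient and gives no ILR versus no-ILR contrast. By arm it offers about 3 events against 162 to 180 with an expected hazard ratio of 1; by receipt one group is empty.

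That the set excludes ILR recipients follows from the definition alone. The sizes rest on the protocol's 1:3 arms, its 5% and below-10% expectations, its 1% annual rate and its 4-year median follow-up. The expected hazard ratio of 1 rests on the Section 10.3 risk assumption; in practice, people who refuse a device may differ from controls in either direction.

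Severity is minor. The sentence is probably a slip for an on-treatment or as-treated set, the analysis is optional, and the primary analysis is untouched.

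**What to change.** Replace the sentence in Section 10.2.5 with a definition that includes ILR recipients and states which groups are compared. Either of two forms would do:
- ILR-arm subjects who received an ILR against all control subjects. Controls who receive an ILR are kept until implantation and censored then; they are not excluded.
- An as-treated analysis with ILR receipt as a time-dependent exposure, which is closer to the present wording because it disregards the randomised arm.

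Whichever is chosen, state how time between randomisation and implantation (up to four weeks under Section 6) and time after explantation are counted, so that event-free waiting time is not credited to the device. Label the analysis supportive.

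The downside should be stated alongside it. Neither form is protected by randomisation. Censoring controls at implantation is probably informative, because Section 3.3 expects such implants generally to follow syncope or suspected arrhythmia.

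The cost is a sentence or two, plus one data check. Section 11.2 already registers ILR-arm subjects not implanted and devices explanted. It does not mention implants in controls. The at-least-yearly look-up of records and registries in Section 7.2.1 should find them, but the sponsor should confirm that their dates are captured. The wording should be settled before the data are analysed.

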#### 10.3 Sample Size Considerations:

We expect that 30% of the participants will have documented AF episodes lasting ≥6 minutes (and per protocol qualifying for OAC) during ILR monitoring for at least three years. The study population is expected to have a stroke rate of 0.7%/year in non-AF patients, and 2%/year in AF patients not treated with OAC. While we expect the number of AF-related strokes to be reduced by OAC, we assume that strokes unrelated to AF will not be influenced by this. We also include the assumption that 3% of all participants in the control group will become diagnosed with AF and start OAC. The annual rate of the primary end point in the control group is thus expected to be 1%. Finally, we expect that 5% in the ILR group will not be monitored due to refusal of ILR implantation or ILR explantation due to discomfort. These patients will participate at the same risk as patients in the control group and will be included in the analysis of the primary endpoint according to the intention-to-treat principle. We thus expect the overall hazard ratio to be 0.65. To analyse this reduction in the primary endpoint with a 2-sided α-level of 0.05 and a power of 80% in a 1:3 intervention:control-randomized population, we will need 279 primary events. Follow-up duration will be adjusted to accommodate the number of primary events. With an assumed length of inclusion period of 1-2 years and a median follow-up up 4 years, 6000 subjects will be needed.

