# **Study Duration:**

The study comprises an inclusion period of approximately 2 years followed by at intervention phase of minimum 3 years. The total study duration will therefore be approximately 5 years.

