# 3.5 Estimated Study Duration

The study is expected to conclude after 3 years of follow-up. The SC will continuously monitor the overall event rate and will recommend if the follow-up period should be extended, based on the number of observed primary endpoints. Based on the event rate the SC may also recommend to alter the sample size in order to complete the trial in approximately 5 years from the start of the recruitment phase.

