# 9.2 Reporting Procedures for All Adverse Events:

All AEs occurring after randomization observed by the investigator or reported by the subject (whether or not attributed to the investigational product), will be reported on the electronic case report form. The following

attributes must be assigned by the investigator:

- Diagnosis.
- Description: E.g. hospital records.
- Dates of onset and resolution and action taking.

The investigator may be asked to provide follow-up information. All AEs, serious or not, that result in a subjects permanent withdrawal from the study must be reported in the CRF. The end-of-study eCRF will be completed, giving details of the withdrawal.

Medically significant AEs considered related to the investigational product by the investigator or the sponsor will be followed until resolved or considered stable.

All deaths occurring in study must be recorded, and cause of death must be investigated. This includes deaths until determination of the study or a maximum of 60 months since enrolment of the subject, whichever is earlier.

It will be left to an investigators clinical judgement as to whether or not an AE is of sufficient severity to require a subjects removal from treatment.

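### At the protocol's own rates, 6,000 subjects with 4 years' median follow-up give about 215 primary events, not 279, and section 10.1 describes an end of study that falls before 279

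*Protocol*

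**What the plan says.** Section 10.3 assumes a 1% annual primary-event rate in controls and adds: "We thus expect the overall hazard ratio to be 0.65". For "a power of 80% in a 1:3 intervention:control-randomized population, we will need 279 primary events". The paragraph ends: "With an assumed length of inclusion period of 1-2 years and a median follow-up up 4 years, 6000 subjects will be needed". Section 10.3 and the synopsis (Statistical Considerations) also say that follow-up will be fitted to the number of primary events.

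The end of the study is described in three places:

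- Section 10.1: "The study is expected to conclude when 279 strokes have occurred or 6,000 study subjects have been followed for at least 36 months", put at about 5 years after the first enrolment.
- Synopsis, Study Duration: about 2 years of inclusion plus at least 3 years, so "The total study duration will therefore be approximately 5 years".
- Section 3.5: "The study is expected to conclude after 3 years of follow-up". The steering committee then watches the event rate and may recommend a longer follow-up or a changed sample size. Section 10.4 gives it the right to do either.

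On deaths, section 9.2 says: "This includes deaths until determination of the study or a maximum of 60 months since enrolment of the subject, whichever is earlier". Section 8.1 collects death data until study termination unless consent is withdrawn, and section 7.2.1 collects adverse events from records and registries to the end of the study.

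**The concern.** Two numbers carry the design: 279 events, which the power depends on, and 6,000 subjects with 4 years' median follow-up, which is meant to produce them. If the second does not produce the first, the stated 80% power does not belong to the trial described. It then matters what ends the trial. Section 10.3 and the synopsis make it event-driven, while section 10.1 offers a calendar alternative joined by an 'or'. Section 10.1 also counts strokes, whereas the endpoint in section 10.2.1 and the target in section 10.3 include systemic arterial embolism. The trial is open-label and its steering committee may receive treatment assignments (section 10.5), so the closing rule should be unambiguous beforehand. If follow-up is prolonged to reach 279, the 60-month limit in section 9.2 also comes into play, and death is the competing event in the principal analysis (section 10.6.2.1).

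**Working it through.** **Inputs.** Two-sided alpha 0.05, power 80%, hazard ratio 0.65, 1:3 allocation, control rate 1% per year (section 10.3), hence 0.65% per year in the ILR group. Arms of 4,500 and 1,500 (synopsis, Sample size). Mortality is not given: 0 is used first, then 2% and 3% per year as assumptions.

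**Step 1: can 279 be reproduced?** (1.960 + 0.842)² = 7.849.

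- Schoenfeld: 7.849 / (0.25 × 0.75 × (ln 0.65)²) = 225.6, so 226 events.
- Freedman with ILR:control ratio k = 1/3: 7.849 × (1 + 0.65/3)² / ((1/3) × 0.35²) = 284.5, so 285 events.

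The stated 279 lies within about 2% of the Freedman figure. A conservative variant of this kind is a plausible basis for it, and 279 itself is not disputed.

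**Step 2: do 6,000 subjects and 4 years give 279?** Without depletion: 4,500 × 0.01 + 1,500 × 0.0065 = 54.75 events per year, or 219 in 4 years. With depletion:

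4,500 × (1 − e^(−0.04)) + 1,500 × (1 − e^(−0.026)) = 176.4 + 38.5 = 214.9.

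This is 77% of 279. Uniform accrual over 2 years with closure at 5 years also gives 214.9. With deaths at rate d, each arm contributes n × r/(r + d) × (1 − e^(−(r + d)t)), averaged over accrual.

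| Scenario (hazard ratio 0.65) | No deaths | 2%/yr deaths | 3%/yr deaths |
|---|---|---|---|
| 1% control rate, 2-year accrual, close at 5 years | 214.9 | 206.4 | 202.3 |
| 1% control rate, 1-year accrual, close at 4 years | 188.5 | 182.0 | 178.9 |
| 1.09% control rate, 2-year accrual, close at 5 years | 233.8 | 224.6 | 220.2 |

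The 1.09% is the unrounded mix from section 10.3 before any anticoagulation in controls: 0.7 × 0.7% + 0.3 × 2%. Every entry is below 279. Even with no treatment effect (1% in both arms) the 4-year total is 235.

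**Step 3: which condition in section 10.1 is met first?** With 1 to 2 years of accrual, the last subject reaches 36 months 4 to 5 years after first enrolment. The first two rows of the table give the events by then: about 179 to 215. So the 36-month condition comes before 279.

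**Step 4: power at the projected events.** The log-rank column uses the expected ILR share of events, π = 0.65/3.65 = 0.178, against 0.25 under the null: power = Φ[(√E × (0.25 − π) − 1.96 × √0.1875) / √(π(1 − π))].

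| Events | Schoenfeld | Freedman 1:3 | Asymptotic log-rank |
|---|---|---|---|
| 189 | 73% | 63% | 64% |
| 215 | 78% | 68% | 70.5% |
| 234 | 81% | 72% | 74% |
| 279 | 88% | 79% | 82% |

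**Step 5: what would deliver 279?** Solving the Step 2 equation for time gives 5.2 years of follow-up without deaths, 5.5 at 2% and 5.7 at 3% mortality. With 2-year accrual, that is 6.2 to 6.7 years after first enrolment. Alternatively, at 4 years and no deaths, 6,000 × 279 / 214.9 = about 7,790 subjects, or a control rate of about 1.31% per year.

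**The case against.** The best defence is that the trial is event-driven. Section 10.1 only says what is expected, section 10.3 and the synopsis say follow-up will be adjusted to the events, and sections 3.5 and 10.4 let the steering committee extend it. This stands against one tempting inference, that the trial as written must stop short of 279. The text permits closure at the 36-month point but does not compel it. It does not repair the projection in section 10.3, nor the conflict with the 'or' in section 10.1, because extension is allowed and not required.

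A reader might also infer from section 9.2 that deaths after 60 months would be lost. The documents do not support that: sections 8.1 and 7.2.1 run to study termination. A count of lost deaths would also need a mortality rate that the protocol does not give. What remains is a contradiction to reconcile.

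Three further points are fair. The synopsis duration (2 years plus at least 3) agrees with a 4-year median, so those two statements do not conflict with each other; they conflict with 279. The power loss depends on the formula: Schoenfeld gives 78% at 215 events, and by the asymptotic log-rank about 265 events would already give 80%. Finally, longer follow-up buys the stated power only if the hazard ratio stays at 0.65. Appendix E gives the device battery three years and section 7.2.1 ends monitoring with the battery, so much of the added time would be unmonitored.

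**Conclusion.** The concern holds as an internal inconsistency. On section 10.3's own inputs, 6,000 subjects with a 4-year median give about 215 primary events without deaths, about 202 to 206 with an assumed 2-3% annual mortality, and at most about 234 with the unrounded control rate. None reaches 279. Power at 215 events is about 68-70% by the methods close to the 279 basis and 78% by Schoenfeld, so any statement of the loss must name its formula. Section 10.1 adds a second inconsistency: at the planned rates its 36-month condition is met first, at about 179 to 215 events, against the event-driven wording elsewhere. These figures assume constant hazards, uniform accrual and no other loss to follow-up. They do not show that the trial will close early or that deaths will go unrecorded.

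**What to change.** 1. **Section 10.3 and synopsis.** Choose one statement. Either 6,000 subjects need a median follow-up of about 5.2 years without deaths (5.5 to 5.7 years at an assumed 2-3% mortality; with 2-year accrual, 6.2 to 6.7 years from first enrolment) for 279 events, noting that this takes the hazard ratio of 0.65 to hold beyond the three-year battery life. Or a 4-year median gives about 200 to 215 events, with the lower power and its formula stated. If the sample is enlarged instead, as sections 3.5 and 10.4 allow, about 7,790 subjects would be needed at 4 years without deaths.
2. **Section 10.1.** Close when 279 adjudicated primary events (stroke or systemic arterial embolism) have occurred and every subject has at least 36 months, or keep the calendar stop and state its expected events and power. Align section 3.5 and the synopsis Study Duration with the choice.
3. **Section 9.2.** Reconcile the 60-month limit with sections 8.1 and 7.2.1 so that deaths are recorded to the end of the study.

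Cost: protocol wording, plus either longer follow-up (already promised in principle, and largely from records and registries) or a less favourable stated power. Neither option in item 1 that keeps 6,000 subjects needs extra patients.
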